Given that PACT collects TOPSE (parental self-efficacy) as part of usual practice, they will collect the questionnaire from participating parents and will share the data with IFF, while IFF research will collect data on the secondary outcome measures (i.e. BAC-C and CPRS) from participating parents through parent-administered surveys. This approach has been taken to keep data collection from participants as minimal as possible in line with ethical good practice.

Parents will be given the questionnaire to fill in on their own without PACT present.

The researchers scoring the data will not be blind to intervention allocation. If the parent reveals their allocated treatment group to the researcher, this will be recorded.

The baseline and follow-up surveys will be sent via email and IFF will follow-up with reminder emails and telephone calls. Parents in the treatment group will complete the endline survey in the final session. PACT will extend the last session by 15 minutes to give parents time to complete the survey. Parents will be encouraged to complete the survey on their own device (e.g. their phone), but PACT will provide an alternative if needed (e.g. using a PACT laptop). Parents and children in one of the Cohort 1 waitlist treatment groups will complete the endline survey during an in-person event (for more information on the event please see the [Experiment 1: Testing use of in-person events](#)). For groups not involved in-person experiment events, parents will be sent the surveys via email by IFF to complete.

The study acknowledges that the different approaches to outcome measure deployment between the treatment group and the waitlist treatment group has the potential to introduce different biases. Though PACT may not be present, the treatment group's TOPSE being organised by PACT for the baseline and endline still may influence responses, for example by increasing the likelihood of socially desirable answers. Conversely, the waitlist treatment group receiving all measures via email may increase the potential of experiencing technical issues filling in the survey or not being able to ask for clarity on questions as they will not be in regular contact with PACT.

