Experiment 2 tests the use of incentives on endline survey completion with Cohort 2 only, in January 2025. Cohort 2 has three treatment groups and two waitlist treatment groups (40 families total). We will explore the effect of offering £10 incentives for endline survey completion with two treatment and two waitlist treatment groups in Cohort 2 (32 families). IFF will randomly select the groups using a random number generator.

Those groups selected will be notified of the opportunity to receive the incentive when they're invited via email to complete the survey. At the end of the survey, they will be able to select from a £10 Amazon voucher or a £10 Love2Shop voucher and asked to provide an email address to receive the voucher. Those selected for the incentive who do not respond to the email prompts will be notified of the incentive when they receive a phone call asking them to complete the survey.

Reporting results: The final report will discuss the results of Experiment 2, specifically, the effectiveness of the incentives by comparing response rates in the treatment group participating in the experiment to response rates in the treatment group not participating in the experiment, and similarly for the waitlist treatment groups.

Cost evaluation

The overall aim of the cost evaluation is to understand the additional costs and, where possible, benefits of the programme compared to if it was not delivered. Our proposed approach is to calculate **the overall cost for BB4K delivery, and the unit cost per family and per each of the three sites.**

Costs will be based on the resources needed to roll out BB4K in comparison to 'business as usual'. In line with the WWCS cost analysis guidance, we will split costs into prerequisites (e.g. access to facilities to deliver, overheads), start-up (e.g. the purchase of equipment, training staff cost, salaries) and recurring delivery costs (e.g. non-durable materials, costs for new staff).

Outside the cost evaluation we will present separately costs of parents' time, children's time, and volunteers' time

As a first step we will calculate the overall costs at BB4K level. We will ask PACT to provide information on the following cost categories:

- Staff costs: including salaries, National Insurance Contributions, pensions for all workers including temporary and contract workers; if staff don't spend all of their time on BB4K, we will ask PACT to confirm the time allocated for the year to BB4K
- Volunteer time, if any

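### Experiment 2 offers the £10 incentive to both Cohort 2 waitlist groups, so the planned waitlist comparison of response rates has no comparator

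*Protocol*

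**What the plan says.** Under Evaluation experiments, Experiment 2, the Protocol sets the scope: "Experiment 2 tests the use of incentives on endline survey completion with Cohort 2 only, in January 2025". It gives the cohort's structure: "Cohort 2 has three treatment groups and two waitlist treatment groups (40 families total"). The incentive is to be explored "with two treatment and two waitlist treatment groups in Cohort 2 (32 families"), and on allocation it says: "IFF will randomly select the groups using a random number generator". Selected groups learn of the voucher by email: "Those groups selected will be notified of the opportunity to receive the incentive when they're invited via email to complete the survey". The results paragraph says that effectiveness will be judged by setting response in the participating treatment groups against "response rates in the treatment group not participating in the experiment, and similarly for the waitlist treatment groups".

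The Randomisation table and the Data collection table both confirm that Cohort 2 has two waitlist groups. The Randomisation table lists them as one group aged 6–11 and one aged 3–5. It lists the treatment groups as two aged 6–11 and one aged 3–5.

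On how the endline reaches treated families, the Data collection section says: "Parents in the treatment group will complete the endline survey in the final session". The section on early impact analysis says the same.

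**The concern.** A comparison of response with and without an incentive needs some families in each condition. In the Cohort 2 waitlist arm every group is given the offer, so the without-incentive condition is empty. No later analysis can recover it, because the gap is created when the offers are made.

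What is at stake is a stated output of the pilot. The two experiments are meant to answer the fourth implementation question, with a focus on raising survey response. The Risks table rates both waitlist retention and low outcome response as medium/high. The waitlist arm is where evidence on incentives would be most useful, and the design gives none there.

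**Working it through.** **Inputs.** Cohort 2 has 3 treatment and 2 waitlist groups (Experiment 2; Randomisation and Data collection tables). Each group has 8 parent–child pairs (Sample size/MDES calculations). The offer goes to 2 treatment and 2 waitlist groups (Experiment 2).

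**The plan's own totals.** Cohort 2: (3 + 2) × 8 = 40 families. Offered the incentive: (2 + 2) × 8 = 32 families. Both stated figures reproduce. The 32 therefore fits two waitlist groups and is not an isolated slip; one waitlist group would have given (2 + 1) × 8 = 24.

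**Split by arm.**

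| Arm | Families | Offered | Not offered |
|---|---|---|---|
| Treatment | 3 × 8 = 24 | 2 × 8 = 16 | (3 − 2) × 8 = 8 |
| Waitlist | 2 × 8 = 16 | 2 × 8 = 16 | (2 − 2) × 8 = 0 |

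**Random selection.** Two treatment groups can be drawn from three in 3 ways. Two waitlist groups can be drawn from two in 1 way, so nothing is being selected at random in the waitlist arm.

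**What the treated comparison can show.** In the comparator group of 8, one family's response moves the rate by 1/8 = 12.5 percentage points. If the group left out is the 3–5 group (1 draw in 3), the incentive is fully confounded with age band. In the other 2 draws, the incentivised set holds both age bands and the comparator is a single 6–11 group.

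**Contrast with Experiment 1.** There, one group per arm attends the event and one does not: 2 × 8 = 16 families with it and 16 without. A near-identical reporting sentence works there because each arm keeps a comparator.

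**Mode of the treated endline.**
- Data collection and the early impact section place it in the final session, which is extended by 15 minutes for the purpose. Cohort 2 delivery runs from September to December 2024.
- Experiment 2 has selected groups, treatment groups included, invited by email in January 2025.
- A sentence in Experiment 1 says that Cohort 2 groups receive their surveys by email. It stands in a section mainly about the follow-up survey, so it does not settle the matter.
- The Data collection table runs the Cohort 2 endline from December 2024 to January 2025, which leaves room for either reading.

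If treated families complete in session, an offer emailed afterwards has little left to act on.

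**The case against.** The strongest defence is that Experiment 2 is a descriptive exercise attached to the implementation evaluation. The primary outcome is TOPSE at follow-up. The endline serves only the early impact analysis, and the Protocol promises a comparison of response rates, not a powered test. All of that stands, and it limits the severity. It does not supply the missing comparator.

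One could read the four named groups as a pool from which incentive groups are then drawn. No second draw or number is stated, and the comparator is defined as groups outside the experiment, which in the waitlist arm is still none. Cohort 1 cannot stand in, because the experiment is confined to Cohort 2.

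A reader might infer three stronger things that the documents do not support:
- **That the experiment can say nothing about incentives.** One treatment group is left without the offer, so a treated comparison of about 16 against 8 families remains.
- **That the offer can reach only treated parents who missed the final session.** This follows from Data collection and the early impact section, but the Experiment 2 text describes email invitations to treatment groups. The supportable point is that these places disagree.
- **That the offer must be randomised to individual families.** This is an option with a trade-off. Treated families meet as a group for 8 or 12 sessions and may compare offers. With all 40 families it would give 20 against 20, and power would still be low. By the arcsine formula, h = (1.960 + 0.842) × √(2/20) = 0.886. From 50%, where 2·arcsin√0.5 = 1.571, the detectable rate is sin²((1.571 + 0.886)/2) = 0.887, or about 89%. The 20 against 20 would not hold if the offer went only to families who had not answered in session. Moving it to the follow-up survey would bring it into the primary-outcome wave.

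**Conclusion.** The point holds for the waitlist arm. As written, the planned comparison is 16 families against 0 and cannot be estimated. This rests only on the Protocol's group counts; the family numbers also assume full groups of eight. The treated comparison exists but is small, rests on one comparator group, and is fully confounded with age band in one draw of three. How treated Cohort 2 families receive the endline is stated inconsistently and must be reconciled before the treated result can be interpreted. The primary TOPSE analysis at follow-up, the randomisation to treatment or waitlist, and the sample size are untouched. The severity is moderate: a certain error in a secondary output, easily corrected before the Cohort 2 endline.

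**What to change.** Offer the incentive to one waitlist group chosen at random from the two. The total becomes 16 treated + 8 waitlist = 24 families, one group of 8 per arm stays without the offer as in Experiment 1, and the waitlist draw becomes a real one with 2 possible outcomes. Report response rates by arm descriptively, with intervals. State one mode and date for the treated Cohort 2 endline, and align Data collection, the early impact section and both experiment sections with it. If both waitlist groups are to keep the offer, delete the waitlist comparison instead.

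The cost is Protocol wording. The maximum voucher spend falls from 32 × £10 = £320 to 24 × £10 = £240. Eight waitlist families lose the offer, which may cost some endline responses if incentives work.

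One limit should be stated in the report. The two waitlist groups differ in age band (6–11 and 3–5), so the restored 8 against 8 comparison is confounded with age whichever group is drawn. Randomising the offer to families within groups (12:12 treated, 8:8 waitlist, up to 20 vouchers) would avoid this, at the price of possible contamination within groups. It is an optional alternative for the team to weigh.

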Difficulties engaging parents and children in qualitative research	Medium/high	High – would affect our ability to report findings on time. Importance of capturing the voice of parents and young people.	Activate recruitment plans immediately upon confirming sampling approach. Provide choice for parents about how to engage (i.e. group-based discussion or one-to-one). Assign large, specialist fieldwork team to schedule interviews. Build in sufficient lead-in times for recruitment. Work closely with PACT and provide them with support they need (e.g. information about the study, etc.). Information will include a convincing rationale for participation and reassurances on confidentiality and how the information will be used. Information will take different formats (e.g. short animation, leaflet) to ensure accessibility. Offer an incentive for taking part.
Difficulties engaging/retaining parents especially in waitlist treatment	Medium/high	There's a risk of attrition especially for the waitlist treatment group due to long delay between randomisation and provision of support	This will be addressed by setting out the requirements for pilot at the outset providing parents and children with clear instructions on what needs to be done and by when. This can be further mitigated by continued communication. Attrition to be monitored and reported according to statistical guidelines.
Low response rates to outcome assessment	Medium/high	There's a risk that parents will not complete all outcome assessments	We selected outcome measures that are relatively easy and quick to fill in; we will provide sufficient data collection window will be given with real-time monitoring.

Risks relating to ethical issues, accessibility, safeguarding, and data protection			
Distress caused to parents/children through the evaluation	Medium	Medium/High – this would be ethically concerning as we aim to provide a positive interview experience and avoid harm. Key consideration for delivery of the evaluation.	Detailed safeguarding plan ensures that participants provide informed consent. Evaluation delivered in line with MRS and GSR ethical guidelines, and in line with Foundations ethical standards. The research team is trained in how to respond to distress and have experience in undertaking similar qualitative research. All staff have enhanced DBS checks and will receive specific training and support. Researchers will offer breaks or end the interview early if participants express strong emotions during the discussion. Design will be approved by the Foundations ethics committee.
Safety and wellbeing of IFF staff	Low	High – this would be ethically concerning. Key consideration for delivery of the evaluation.	Committed to safeguarding and promoting the wellbeing of our team. Wellbeing committee runs regular activities to promote, and we have a team of seven mental health first aiders. Brief interviews on how we will ensure interviewer safety and wellbeing.
Data security breach, leads to sensitive information being released/shared	Low	Very High – for this specific audience, disclosure of personal data is a particular concern due to the risk of re-victimisation. Even a perceived risk of this may lead to distress and worry for participants.	Stringent data security measures are in place and IFF holds ISO 27001:2013 and CyberEssentials Plus accreditations. All sensitive files are held on secure servers with access restricted to the core research team. Any transfer of sensitive data will be encrypted. We would minimise the data we held and encrypt files containing contact details even within our secure server, to further reduce any risk in the event of a breach.
Risks relating to quality			

Unmanageable burden on BB4K staff around evaluation	Low/Medium	High – would affect our ability to report findings on time and our ability to answer evaluation questions.	Clear strategy and ongoing communication with BB4K. Assessment of existing data to avoid duplication of data collection. Commitment to working flexibly and collaboratively with the BB4K team to minimise burden.
Outcome measures are not optimal	Low/Medium	Outcome measures do not align with the theory, are difficult to administer, or measure a change that cannot be realised within the timeline.	Our experienced team will ensure that outcome measures are fit for purpose. This includes expert assessment and consultations with PACT to allow us to select the most robust instruments.

Timeline

Dates	Activity	Staff responsible/ Leading
January to April 2024	Onboarding and set-up (including evaluation protocol, ethics and data protection)	IFF Research
April to May 2024	Cohort 1 delivery set-up, randomisation and baseline survey (2 research/treatment groups and 2 non-research/waitlist treatment groups)	IFF Research/PACT
May to July 2024	Cohort 1 group delivery (2 groups of aged 6-11s) – 8 sessions over 10 weeks	PACT
July 2024	Cohort 1 endline survey	IFF Research
June to August 2024	Implementation and process evaluation Wave 1	IFF Research
September to October 2024	Cohort 1 follow-up survey	IFF Research
January to March 2025	Cohort 1 waitlist treatment group delivery	PACT
August to September 2024	Cohort 2 delivery set-up, randomisation and baseline survey (3 research/treatment groups and 2 non-research/waitlist treatment groups)	IFF Research/PACT
August 2024	Cost evaluation data collection Wave 1	IFF Research
September to December 2024	Cohort 2 group delivery (2 groups of aged 5–11s; 1 group age 3–5)	PACT

December 2024	Cohort 2 endline survey	IFF Research
November 2024	Mid-point grant progress report	IFF Research
December 2024 to January 2025	Implementation and process evaluation Wave 2	IFF Research
January to March 2025	Interim report	IFF Research
March 2025	Cohort 2 follow-up survey	IFF Research
April 2025	Cost evaluation data collection Wave 2	IFF Research
May to September 2025	Final reporting	IFF Research
